In the early 20th century, carbohydrates were discovered to be a crucial source of energy for exercise(1). During prolonged endurance exercise, carbohydrate intake helps maintain blood glucose concentrations, exercise reaction times, and technical performance(2, 3). However, even during shorter, higher-intensity exercise (e.g., < 1 hour, 75% $\dot{V}O_2\text{max}$), carbohydrate intake can improve exercise performance(1). For this reason, muscle glycogen depletion is not considered a performance-limiting factor, and other factors may enhance performance during high-intensity exercise(4).

Studies have had participants gargle an aqueous solution of CHO in the oral cavity for several seconds and spit it out. This method was associated with improved performance during endurance activities(5). During mouth rinsing, the CHO in the aqueous solution travels to the neural sensors in the oral cavity, which improves the performance of the nerve signals transmitted to the brain; this provides indirect evidence of the strengthening of the central nervous system effect(4). Rinsing the mouth with CHO solution and then spitting it out can also prevent gastrointestinal discomfort caused by the ingestion of CHO and the conflict between improving sports performance and the ingestion of CHO for those with weight control needs; this method also provides new reference for the supplementation of CHO in sports performance.

A study on aerobic exercise conducted a long-distance cycling test after participants gargled a 6.4% CHO solution. During exercise, the average power, overall power, and climbing power increased, and perceived levels of fatigue decreased(6). However, studies on the effects of CHO-solution mouthwashes on short-term, high-intensity exercise and resistance training have yielded inconsistent results. Decimoni et al. (2018) discovered that rinsing the mouth with a CHO solution before resistance exercise can reduce fatigue and enable weightlifters to lift heavier loads during resistance exercise(7). However, another study observed that gargling different doses of CHO solution (6%, 12%, and 18%) before resistance exercise did not improve maximal muscle strength or muscle endurance(8). Whether rinsing the mouth with CHO solution before resistance exercise improves performance remains to be further explored. On the other hand, it remains to be studied whether chewing caffeinated gum can also enhance inertial resistance exercise performance.

Flywheel resistance training, a type of eccentric load training, has been widely discussed and used for various sports. In flywheel resistance training, inertial power generated by the flywheel during muscle acceleration and deceleration provides resistance in the eccentric and concentric phases, respectively(9). The flywheel has been demonstrated to improve health and athletic performance and prevent sports injury(10). No studies have examined the effect of rinsing the mouth CHO solution on the performance of inertial resistance exercise. For this reason, this study investigated the effect of carbohydrate mouth rinsing (CMR) on inertial resistance exercise performance.

Methods

Participants

This study recruited 20 healthy adult men (age: 22.4±3.7yr, height: 171.3±5.9cm, weight: 76.4±11±kge). The inclusion criteria were (1) regular weight training habits, (2)

familiarity with Romanian deadlift movements, and (3) no chronic diseases such as hypertension, diabetes, and kidney disease or sports injuries such as lacerated knee ligaments, inflammation and rupture of tendons, strained biceps femoris or quadriceps, and strained biceps within the 6 months prior. Those who (1) did not have regular exercise habits, (2) were unfamiliar with Romanian deadlift movements, and (3) had certain health problems that prevented them from performing exercise or injury from which they had not recovered for more than 6 months were excluded. Before the experiment, the researchers explained the experimental procedure to the participants and obtained their informed consent. This study was approved by the Human Subject Research Ethics Committee of Jen-Ai Medical Foundation (111-09). This study was conducted in accordance with the Declaration of Helsinki.

Experimental design in study 1

This study conducted a randomized crossover trial with a single-blind experimental design. All participants were subjected to two experimental conditions, one with CMR and a placebo trial (PL). The CMR was a colorless and odorless 6.4% maltodextrin solution, and mineral water was used for the PL. After at least two introductory sessions, the participants were randomly divided into two experimental sequences, CMR-PL or PL-CMR, by using a crossover design. The second phase of the experiment was held after 7 days of rest and recovery to eliminate the effects of muscle fatigue and delayed muscle soreness.

Experimental design in study 2

This study conducted a randomized crossover trial with a single-blind experimental design. All participants were subjected to two experimental conditions, one with CAF and a placebo trial (PL). The CAF was chewing the caffeinated gum containing 200 mg for 20 minutes, and placebo gum was used for the PL. After at least two introductory sessions, the participants were randomly divided into two experimental sequences, CAF-PL or PL-CAF, by using a crossover design. The second phase of the experiment was held after 7 days of rest and recovery to eliminate the effects of muscle fatigue and delayed muscle soreness.

Pretests

Two pretests were conducted before the formal experiment. The pretests involved familiarization with the experimental apparatus, practicing the movements, and testing with different inertia loads. The load resistance was 0.010, 0.025, 0.050, or 0.075 kg, and the participants' peak power was used as the experimental load resistance. The

pretests were separated by 7 days, and the first phase of the formal experiment and the last pretest were also separated by 7 days to allow for adequate recovery of muscle performance.

The participants used an Exxentric inertial resistance training machine (Exxentric kbox 4 Pro, Stockholm, Sweden) to complete the Romanian deadlift movement test. With the maximum inertial resistance measured during the pretest being used as the resistance load during the experiment, the participants underwent maximum inertial resistance training comprising five sets of five reps, with a 3-min rest between.

The second pretest involved the same procedure as the first pretest but with the participants using the load resulting in the highest power output identified during the first pretest; the pretests were conducted at least 48 h apart. Before each test, the participants underwent a standardized warm-up supervised by the individual conducting the experiment, which included riding on a stationary bicycle with a speedometer for 5 minutes (at a manageable intensity, that is, in the 10–12 range on the perceived exertion scale, with the full range being 6–20), a joint range of motion warm-up, and dynamic stretching for 3 min. Before the warm-up, the scale was explained.

Formal experiment

The participants were required to arrive at the laboratory at 3:30 p.m. on the day of the experiment, fast for at least 3 hours beforehand, and avoid high-intensity training (e.g., weight training, endurance training, and high-intensity interval training) for 3 days before the experiment. All groups were required to consume the same food 24 hours before the experiment and avoid caffeine, alcohol, energy drinks, and any form of stimulant or other substance that would affect exercise performance.

Before the first experiment, the participants performed a standardized warm-up, comprising riding on a stationary bicycle for 5 minutes, joint range of motion warm-up and dynamic stretching for 3 min, and one set of eight reps of Romanian deadlifts with the flywheel; the load resistance was 0.01 kg. The participants rinsed their mouths with either 25 ml of CHO solution or the placebo solution for 20 seconds and spit the solution into a designated container after rinsing. Next, the participants used the inertial resistance training machine to complete the Romanian deadlift movement test. With the maximum inertial resistance measured during the pretest being used as the resistance load during the experiment, the participants completed maximum inertial resistance training comprising five sets of five reps, with a 3-min rest between. A 0.6-kg training bar was attached to the inertial resistance training machine during each testing session. To standardize the participants' range of motion during testing, a piece of tape was placed at the midpoint between the tibial trochanter and talus to indicate the range of

motion for the Romanian deadlifts, with the endpoint being full hip extension. The process was as follows:

1. Participants stood over the tether with their feet hip-width apart, toes pointing forward, and head and eyes facing straight ahead.
2. Hands were positioned shoulder-width apart, naturally lowered, with a positive grip on the training bar.
3. The training bar was connected to the tether, which was connected to the flywheel shaft through a hole in the platform, and the movement began in the bent position (i.e., at the designated starting point of the range of motion). The participants pushed back on their gluteus maximus and kept their back straight, their shoulders pulled back, and their chest up.
4. Each movement started with the concentric phase and ended with the eccentric phase.
5. In the concentric movement phase, the crossbar was pulled along the thigh, and the tether was pulled to put the flywheel in motion. Participants contracted the gluteus maximus, hamstrings, and lower back muscles until the hip joint was fully extended to the end position.
6. During the eccentric movement stage, the flywheel rotated, and the motion decelerated from the end position through centrifugal muscle contraction. Participants then completed the motion and returned to the starting position through a braking motion.
7. These steps were repeated until the test was complete.
8. The participants were instructed to not shrug their shoulders when their hip joints were fully extended and not allowed to flex their ankles.
9. The participants began resisting the inertia in the first third of the concentric movement and then stopped moving at the end of the range of motion with maximum effort; the participants were instructed to perform the concentric movements quickly.

Before each set, participants performed one test movement to increase the power of the flywheel, followed by five test movements, and they were verbally encouraged throughout the test. These initiated the movement of the flywheel and increased its speed, and the resulting data were excluded from statistical analysis. In the second experiment, which was conducted 7 days later, the participants repeated the steps from the first experiment.

The participants' test data were measured using Kmeter, fed back to the system, and transferred to an Android device (ASUS ZenFone 6) over Bluetooth for storage. The data were then exported to a computer in comma-separated value format for statistical analysis. The researchers analyzed data on seven factors measured using the Kmeter feedback system: power, concentric peak power, eccentric peak power, average force, average speed, peak speed, and total work.

Carbohydrate solution and placebo

In the experiment, the carbohydrate solution was prepared by dissolving 6.4 g of colorless and odorless maltodextrin in 93.6 mL of water; the mixtures were then adjusted to a 6.4% maltodextrin solution for the participants to rinse their mouths; the placebo group rinsed their mouths with drinking water. All carbohydrate solutions were prepared by the principal investigator of the research project before the experiment, and they were similar to the placebo in appearance and taste to ensure that the participants could not distinguish them. Mouth rinsing was defined as distributing the carbohydrate solution around the mouth for a few seconds followed by spitting it out into a designated container. The most commonly used carbohydrate solutions are glucose and water-soluble maltose dextrin at a 6.4% concentration(11), which are used for 15–20 seconds before exercise. Thirteen participants correctly guessed they were on carbohydrate (65%) and nine participants correctly guessed they were on placebo (45%).

Caffeine gum

The experimental group of caffeine gum will use the U.S. Army's caffeine gum (Military Energy Gum-StayAlert, Arctic Mint flavour; Chicago, IL) as the experimental group. Caffeine gum contains 100mg of caffeine.

Excentric kbox 4 Pro

Many studies have described the mechanical advantages of flywheel devices and their effects on neurophysiological mechanisms, muscle morphological adaptation, and training during acute and chronic conditioning(12); this has stimulated an interest in the benefits of flywheel exercise in athletic training, injury prevention, and clinical rehabilitation among researchers and practitioners(13).

In inertial resistance training, flywheel inertia is used to generate eccentric force, enabling eccentric muscle training. The muscle groups that can be trained through this method include the triceps, biceps, gluteus maximus, quadriceps, back, and calves. Data on at least five factors (average power, concentric peak power, eccentric peak power, overload peak, and average force) can be measured using the Kmeter feedback system and presented as a bar graph in the app. The system can also be used to measure displacement distance, average speed, peak speed, total work (in joules), number of reps, and average rep time.

Statistical analysis

The data are presented as means \pm standard deviations, and the analysis was performed using SPSS (version 20, Chicago, IL, USA). The Shapiro–Wilk test was

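### Does the protocol set the test load by two different rules, highest power and largest inertia?

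*Protocol*

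**What the plan says.** The Pretests section gives the candidate loads: "The load resistance was 0.010, 0.025, 0.050, or 0.075 kg". It describes the load for the experiment in two ways.

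- **By power.** The section states that each man's "peak power was used as the experimental load resistance". A few sentences later it has the second pretest run with "the load resulting in the highest power output identified during the first pretest".
- **By inertia.** Between those two statements, the same section says: "With the maximum inertial resistance measured during the pretest being used as the resistance load during the experiment, the participants underwent" the five sets. The Formal experiment section uses almost the same sentence for the outcome sessions: "With the maximum inertial resistance measured during the pretest being used as the resistance load during the experiment, the participants completed" the sets. It does not mention power as the basis for the load.

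For the second session, the Formal experiment section says that "the participants repeated the steps from the first experiment". Both design sections (study 1 and study 2) place the random allocation to sequence after the introductory sessions.

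**The concern.** Highest power and largest inertia are different criteria. A man may produce his highest power at a small or middling inertia, and then the heaviest inertia on the list is not his highest-power load. The power sentence also needs interpreting before it can be used, because power is an outcome and not a load. No sentence says that the two descriptions mean the same thing, and the section that governs the outcome sets carries only the inertia wording.

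All seven Kmeter outcomes (average power, the two peak powers, force, the two speeds and work) are recorded at this load. If the rule is unclear, a reader may not know whether an effect of the carbohydrate rinse or the caffeine gum applies at each man's highest-power inertia or at the heaviest inertia offered.

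**Working it through.** The protocol states no figure for this point, so there is none to reproduce. The check has three parts.

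**1. How far apart the two readings can be.** The inputs are the four inertias in the Pretests section: 0.010, 0.025, 0.050 and 0.075. Assume that every man tries all four. The literal inertia rule then selects 0.075 for everyone, and the power rule selects the inertia at which his power peaked. The ratio is 0.075 divided by that inertia.

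| Inertia at which power peaks | Ratio, inertia rule to power rule |
|---|---|
| 0.075 | 0.075 / 0.075 = 1 |
| 0.050 | 0.075 / 0.050 = 1.5 |
| 0.025 | 0.075 / 0.025 = 3 |
| 0.010 | 0.075 / 0.010 = 7.5 |

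The ratios do not depend on the unit printed. The protocol has no criterion for failing a load, so there is no basis for cases in which a man's heaviest load is below 0.075. It also gives no pretest power data, so how many of the 20 men fall in each row cannot be calculated. The number for whom the readings differ lies between 0 and 20.

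**2. Which reading fits the text.** Take the statements in the order in which Pretests gives them: load tied to peak power; load as the greatest inertial resistance found at the pretest; second pretest at the load of highest power. All three concern a load that the pretests yield for each man.

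Under the literal inertia reading, everyone who tried the full list would be tested at 0.075. The pretest would then have nothing individual to measure, and rehearsing at the highest-power load in the second pretest would serve no clear purpose. If the middle sentence is shorthand for the inertia of maximum power, all three statements agree and the pretest has a function. The same sentence also applies the word for maximum to the training itself, which suggests loose usage.

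**3. What the ambiguity could do to the analysis.** Write *L* for the load assigned to a man, under whichever rule. His contribution to the paired t-test is

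*d* = outcome on active at *L* − outcome on placebo at *L*.

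- *L* comes from the pretests, which precede allocation to sequence, so it cannot depend on the treatment or on its order.
- The Formal experiment section sets one pretest-derived load for the experiment and has the second session repeat the first, so the same *L* enters both terms.
- If treatment has no effect, *d* has mean zero whatever *L* is, given the usual crossover assumptions about period and carry-over, which do not involve the load rule.

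The choice of rule therefore does not bias the paired difference or alter its type I error. The size of a true effect might differ between inertias, but that concerns the setting to which the result applies, not the validity of the comparison.

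**The case for a change.** The strongest case for acting is that the load is a core test condition and belongs in the protocol, so a statistical analysis plan that is not at hand would not excuse the inconsistency. Someone running a session from the Formal experiment section alone would see only the inertia wording and could reasonably mount the heaviest flywheel load. The authors could state the power rule plainly, as they did for the second pretest, yet did not do so for the formal test. One common wording and a count of men per inertia would cost almost nothing.

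Part of this stands. The two wordings do differ, nothing in the text equates them, and the Formal experiment section read alone could mislead. Nor does the protocol say which power measure would pick the load.

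It does not stand as a reason to change the plan. The contrast drawn for the second pretest may simply be with trying all four loads, so it is not evidence that a separate rule was meant for the formal test. A single wording would leave the design, the sample size, the outcomes and the paired comparison as they are. Anyone writing up the trial would in any case describe the load from the session records.

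**Conclusion.** No change to the plan is called for. This is a clerical inconsistency in how one quantity is described. Read together, the statements in Pretests point to a single individually measured load, with the inertia phrase most coherently taken as a loose form of the power wording. That is a judgement about what the text most likely means. It is not a view on which load ought to be used.

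If the literal reading were nonetheless the one applied, a man's inertia would be 1.5 to 7.5 times his highest-power inertia wherever the readings differ, assuming that all four loads were tried. The number of men concerned is unknown and could be 0. Under either reading the within-man comparison of active and placebo remains unbiased with respect to the load. This rests on two points: the load is fixed at the pretests before allocation, and the second session repeats the first. The first follows from the order of events in the design sections, and the second is stated in Formal experiment. The only loss is some precision in describing the load to which the effects apply, which is a matter for reporting.

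### Single-blind design with verbal encouragement in a maximum-effort test: nothing in the stated design guards against encouragement that differs by condition

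*Protocol*

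**What the plan says.** The sections on experimental design for Study 1 and for Study 2 open with the same sentence: "This study conducted a randomized crossover trial with a single-blind experimental design". Neither names who is blinded.

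For Study 1, the section on the carbohydrate solution and placebo explains the masking. The rinses are made alike so that participants cannot tell them apart. The same section states: "All carbohydrate solutions were prepared by the principal investigator of the research project before the experiment". For Study 2, the design section says that "placebo gum was used for the PL". No section describes masking of the people who run the tests.

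The Formal experiment section describes the session for the rinse: "The participants rinsed their mouths with either 25 ml of CHO solution or the placebo solution for 20 seconds". The lifting instructions ask for each movement to be "stopped moving at the end of the range of motion with maximum effort", and during the sets "they were verbally encouraged throughout the test". A week later, "the participants repeated the steps from the first experiment".

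Seven outcomes are then taken from the Kmeter system. The Statistical analysis section compares them between carbohydrate rinse and placebo with a paired-samples t-test.

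**The concern.** In a test of maximal voluntary effort, what is measured depends on how hard the participant tries, and encouragement is a direct human influence on that. If the person encouraging knows the condition, the encouragement may be warmer, louder or better timed in one condition than in the other, without any intention. That is performance bias. It acts on the effort itself, before the device records anything.

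At stake is the comparison of active with placebo on all seven Kmeter outcomes. Heart rate and perceived exertion are not part of this point.

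Single-blinding is a stated design choice, not a detail left for later. Who is masked, and how a maximum-effort test is conducted, belong in the protocol. A statistical analysis plan could not repair them once the data are collected.

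**Working it through.** No figure in the protocol depends on this point, so there is none to reproduce. The check sets the relevant statements side by side and then asks whether the design or the analysis would remove the bias.

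**1. What is protected.**

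| Feature | Stated control |
|---|---|
| Participant's knowledge of the rinse | Solutions alike in appearance and taste |
| Warm-up | Standardized |
| Range of motion | Marked with tape |
| Resistance load | Set from the pretest |
| Presence of encouragement | Given throughout the test; steps repeated in the second session |
| Wording, timing and intensity of encouragement | None stated |
| Encourager's knowledge of the condition | None stated |

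Both sessions are encouraged, so the gap is not encouragement in one session only. What stays open is its manner, and whether the person giving it is masked.

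**2. Whether the crossover and the t-test remove it.** For one participant, let τ be the true effect of active against placebo, π the effect of the second period against the first, and b the shift in performance caused by encouragement that differs by condition. The expected active-minus-placebo difference is:

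- sequence active then placebo: τ + b − π
- sequence placebo then active: τ + b + π

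With equal numbers in the two sequences (an assumption; the protocol does not give the split), the average is ½[(τ + b − π) + (τ + b + π)] = τ + b. The period effect cancels. The encouragement shift does not, because it follows the condition. Stable differences between men also cancel within each pair, but b arises within each man. The paired t-test therefore tests τ + b, not τ.

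**3. Whether recording by device removes it.** The Kmeter prevents an observer from misreading a result. It records the effort that was made, including any part of it that encouragement produced.

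**4. Whether a size can be given.** That would need b and the SD of the paired difference. The protocol reports neither, nor anything on how encouragement varied. Any false-positive rate would rest entirely on an assumed shift, so none is offered.

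**5. Which study it covers.** The Formal experiment section describes the rinse session only, and the t-test is specified for carbohydrate rinse against placebo. No separate test procedure is given for the gum. The point carries over to Study 2 only if the same procedure was used there.

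**The case against.** The strongest objection is that the key link is missing from the text. Bias by this route needs an encourager who knows the condition, and the protocol does not say who encouraged or what they knew. The rinse is described as colorless and odorless, so a tester who did not prepare it could hardly recognize it. Preparation is assigned to the principal investigator. A "standardized warm-up supervised by the individual conducting the experiment" is mentioned under Pretests, but nothing shows that this individual was the preparer or the encourager. This stands. A reader might infer that the investigator who mixed the solutions also encouraged the lifts, or that staff knew the condition. The documents support neither.

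A second objection is that this is mere omission: single-blinding is openly declared, and a script is operational detail. This stands only in part. The declared design promises masking of one party, and the masking described is for participants. The protocol thus chose a weaker form of blinding for an outcome that depends on effort and encouragement, while a stronger form was within reach. It says the rinses already look and taste alike, and its reference list includes a caffeine study on a flywheel device whose title calls it double-blind.

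A third objection is that the trial reads as completed, so coding and scripts come too late. For Study 1 this is probably right, since participants' guesses are already reported. For Study 2 the tense is mixed: the design is in the past tense, but the Caffeine gum section uses the future. For finished sessions only disclosure remains. That part is a reporting matter and does not carry the point.

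The reported guesses might be read as evidence on either side. They concern participants in Study 1, not staff, and they neither test nor size an effect of encouragement.

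**Conclusion.** The point holds as an open route for performance bias. The stated design does not protect against encouragement that differs by condition, and neither the device, the crossover nor the paired t-test would remove the resulting shift.

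The conclusion rests on two readings. The first is that single-blind here means participants only, since no other masking is described. The second is that a maximum-effort result can respond to encouragement. For the gum study it also depends on the same test procedure having been used. If the tester was in fact masked, one sentence in the protocol would settle most of the concern.

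A reader might go further and infer that the results are biased in favour of the active condition. The documents do not support that: they give no evidence that encouragement differed, no direction and no size. Confidence is medium. The change should be made where sessions remain to be run, because it is cheap and protects all seven Kmeter outcomes.

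**What to change.** For sessions still to be run:

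1. Change single-blind to participant- and tester-blind. Supply the active product and the placebo in identical coded containers. The preparer holds the code and does not run or encourage the tests.
2. Use one fixed encouragement script, with the same words at the same repetitions, in both conditions. This helps even if a tester learns the condition.
3. State in the protocol who encourages, and whether the same test procedure applies to the gum study.

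For completed sessions, state who encouraged, whether they knew the condition and whether the wording was fixed. If the encourager was not masked, limit the conclusion accordingly.

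The cost is labels, a code list and a one-page script. Separating preparation from testing may mean reassigning existing staff, but no additional person is asked for. For completed sessions the cost is a few sentences.
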